6.5 Justification for Exclusion of Special Populations

6.5.1 Justification of Exclusion of Pregnant Women

Pregnant women are excluded from participation in this study. The effects of Pfs230D1-EPA/Matrix-M on the developing human fetus are unknown with the potential for teratogenic or abortifacient effects.

6.5.2 Justification for Exclusion of Children

This is a "first-in-human" trial with the Pfs230D1-EPA/Matrix-M vaccine. As such, safety and tolerability should be established in adults prior to testing in children.

7 Study Agents

7.1 Pfs230D1-EPA/Matrix-M

7.1.1 Manufacturing

Pfs230D1M-EPA: PpPfs230D1M and EcEPA lots, both manufactured at the Pilot Bioproduction Facility, Walter Reed Army Institute of Research (Silver Spring, Maryland) in current Good Manufacturing Practices (cGMP) compliance, were used to manufacture the conjugate. PpPfs230D1M is a *Pichia*-expressed recombinant subsegment (S542-G736) of Pfs230 with a molecular mass of 21,854 daltons. EcEPA is an *Escherichia coli*-expressed recombinant protein with a molecular mass of 66,975 daltons. The Pfs230D1M-EPA conjugate was produced by reaction between thiolated PpPfs230D1M and maleimide-activated EcEPA, followed by purification using size-exclusion chromatography. The Pfs230D1M-EPA conjugate was manufactured at the Walter Reed Army Institute of Research Pilot Bioproduction Facility in compliance with cGMP standards.

Matrix-M: The Matrix-M adjuvant is manufactured by Novavax AB (Uppsala, Sweden), a subsidiary of Novavax, Inc. The adjuvant contains purified saponin components derived from an extract of the bark of the Quillaja saponaria tree; a phospholipid, egg-derived phosphatidylcholine (PC); and semi-synthetic cholesterol of non-animal origin. The manufacturing process starts with extraction of the Quillaja bark to provide the Quillaja extract which is fractionated by chromatography into two distinct fractions (Matrix-A and Matrix-C).

7.1.2 Disposition and Dispensation

The Pfs230D1M-EPA vials will be supplied to the study site pharmacist by the Sponsor or Sponsor representative. The Sponsor receives the product from the Pilot Bioproduction Facility, Walter Reed Army Institute of Research (Silver Spring, Maryland) where the materials are formulated and packaged, or from ThermoFisher BioServices (Gaithersburg, Maryland) where additional product manufactured at the Biopharmaceutical Development Program at the Frederick National Laboratory of Research is stored.

The adjuvant will be supplied under refrigerated conditions (2°C to 8°C) for mix with Pfs230D1M-EPA at the site. Vials and cartons containing the adjuvant will be labelled as appropriate. See Section 7.8 for information about study agent accountability.

7.1.3 Formulation, Packaging, and Labeling

Each single-use vial of Pfs230D1M-EPA contains 160 μ g/mL of conjugated Pfs230D1M and 124 μ g/mL or 143 μ g/mL of conjugated EPA in 4-mM phosphate-buffered saline (PBS), in a volume of 0.5 mL. The vial label reads "160 μ g/mL Conjugated Pfs230D1M in 4-mM PBS." Vaccines will be labeled "Caution: New Drug – Limited by Federal (or United States) law to investigational use."

The active ingredient in Matrix-M, specifically Matrix-M1, are saponin-based fractions. Matrix-M1 has a ratio of Matrix-A and Matrix-C of 85:15 (by weight). Both Matrix-A and Matrix-C are individual fractions (separated by chromatography) derived from extracts from the *Quillaja saponaria* tree. Each vial of Matrix-M1 contains saponin content of 0.375 mg/mL in PBS, at a pH of 7.2, in a final volume of 0.75 mL. The Matrix-M1 adjuvant is analyzed according to set specifications for saponin content (Matrix-A and Matrix-C) by reversed-phase high-performance liquid chromatography (RP-HPLC), appearance, turbidity, endotoxins, and sterility. The adjuvant is supplied for on-site reconstitution under refrigerated conditions (+2-8°C).

Formulation for each dose level

Final High Dose DP:

Pfs230D1-EPA/Matrix-M

107 µg/mL Pfs230D1

+125 µg/mL Matrix-M in

0.75 mL volume

40 µg Pfs230/50 µg MM

High Dose Cohort

Deliver 400 µL

42.7 µg Pfs230+50 ug Matrix-M)

Figure 18 provides an illustration of the formulation of Pfs230D1M-EPA and Matrix-M for each of the three dose levels of vaccine.

160 µg/mL in 0.5 mL vial USP Sterile Saline (0.9%)Addition of 250 µL MM Dilution with Dilution with 200 µL NaCl 1600 ul Matrix M NaCl Addition of 0.375 550 uL MM ma/mL

Final Mid Dose DP:

Pfs230D1-EPA/Matrix-M

64 µg/mL Pfs230D1 +165

µg/mL Matrix-M in 1.25 mL

volume

Middle Dose Cohort

20 µg Pfs230/50 µg MM

Deliver 300 µL

(19.2 µg Pfs230+50 ug Matrix-M)

Addition of

Final Low Dose DP:

Pfs230D1-EPA/Matrix-M

32 µg/mL Pfs230D1 + 60

ug/mL Matrix-M in 2.50 mL

volume

12.5 µg Pfs230/25 µg MM

Deliver 400 µL

12.8 µg Pfs230+24 µg Matrix-M

Low Dose Cohort

Figure 18. Formulation of Pfs230D1M-EPA and Matrix-M for each dose level of Pfs230D1-EPA/Matrix-M vaccine.

7.1.4 Storage, Shipping, and Stability

Study vaccine Pfs230D1M-EPA must be stored at -65°C to -90°C except during vaccine transports (on days of vaccination/use), when the range must remain within -60°C to +9°C. This allows for the vaccine to thaw during transport to the field. The vaccine is then stored at 2-8°C until use, and cannot be refrozen for later use. Once thawed, the vaccine vial must be labeled and quarantined as unusable. Shipping specifications in the standard operating procedures (SOPs) allow for a range of -90°C to -40°C for dry ice shipments. However, the long-term storage in a freezer cannot exceed -65°C. Vaccines are always shipped on dry ice, and generally remain below -70°C. The container with Matrix M1 is stored at +2-8°C until use.

Vials will be transported and stored at temperature-controlled conditions, according to SOPs. Temperature data loggers will accompany the vaccines at all times to ensure storage temperature limits have not been violated. Refrigerator and freezer temperatures will be continuously monitored. Access to study vaccine will be limited to authorized study personnel. Any temperature excursion outside the defined range must be reported to the Sponsor. The impacted products must not be used and must be stored in quarantine at indicated temperature conditions until usage approval has been obtained from the Sponsor.

7.1.5 Preparation and Dosage

The Pfs230D1M-EPA conjugates are stored at -65°C to -90°C until just before transport to the field for use, then stored at 2-8°C as described above. The final vaccine for administration is obtained by admixing Pfs230D1M-EPA with Matrix-M as appropriate for each dose level (see Figure 18) and must be administered within 4 hours of reconstitution. See Section 7.3 for administration information.

7.2 Comparator vaccine

7.2.1 Manufacturing

Verorab Rabies Vaccine is manufactured by Sanofi Pasteur.

7.2.2 Disposition and Dispensation

Verorab Rabies Vaccine will be supplied to the study site according to the manufacturer's recommendations. See Section 7.8 for information about study agent accountability.

7.2.3 Formulation, Packaging, and Labeling

Verorab Rabies Vaccine is a purified inactivated rabies vaccine (Wistar rabies PM/WI 38 1503-3M strain) prepared on Vero cells. It is supplied as a powder and solvent for suspension for injection in a prefilled syringe. Before reconstitution, the powder is a white and homogeneous pellet. The solvent is a limpid solution.

7.2.4 Storage, Shipping, and Stability

The product should be stored in the original outer package, refrigerated (2°C - 8°C), and protected from light. It should not be frozen. After reconstitution, the vaccine may be used up to 8 hours after reconstitution provided it is maintained at 2°C to 8°C and protected from light. Unused vaccine must be discarded after 8 hours.

7.2.5 Preparation and Dosage

Verorab Rabies Vaccine should be reconstituted immediately prior to use, according to instructions provided in the package insert. After reconstitution, 1 dose (0.5 mL) contains rabies virus, WISTAR Rabies PM/WI38 1503-3M strain (inactivated) ≥ 2.5 IU.

7.3 Administration

Each dose of the Pfs230D1-EPA/Matrix-M vaccine or Verorab (or other rabies vaccine approved by Malian health regulatory) is administered as an IM injection into the deltoid muscle. Arms may be alternated with successive vaccinations. When choosing an arm for the vaccine injection, clinicians should consider whether there is an arm injury, local skin problems such as scarring or rash, or significant tattoo that precludes administering the injection or will interfere with evaluating the arm after injection. In keeping with the MRTC practices and procedures and good medical practice, acute medical care will be provided to subjects for any immediate allergic reactions or other injury resulting from participation in this research study.

7.4 Contraindications to Vaccination

The following criteria should be checked prior to each study vaccination and are contraindications to further vaccination with either the experimental vaccine or the rabies vaccine:

- Hypersensitivity reaction following administration of the study vaccine or comparator.
- Positive urine or serum β-hCG test prior to vaccination.

Subjects who receive at least 1 dose of study vaccine under this protocol prior to developing a contraindication will be encouraged to remain in the study for safety evaluation of the dose(s) already received and complete research visits for immunogenicity and functional activity if deemed safe by the PI. Subjects who have a positive β -hCG test prior to their first study vaccination may be withdrawn from the study and replaced.

7.5 Indications for Deferral of Vaccination

If any of the following criteria are met at the time of the scheduled study vaccination, the vaccination will be deferred pending resolution of the issue:

- Oral temperature >38.0°C at the time of vaccination.
- Receipt of a prohibited medication/procedure as described in Section 7.7.

Any other condition that in the opinion of the investigator poses a threat to the individual
if immunized or that may complicate interpretation of the safety of vaccine following
immunization.

Symptomatic individuals may be followed in the clinic until the symptoms resolve or the window for immunization expires. No further vaccination will be performed if the subject does not recover (i.e., temperature ≤38.0°C and/or lack of symptoms) within the vaccination window.

If the subject meets any of the above criteria for deferral on the day of first immunization, the investigator may elect to withdraw the subject from further participation in the study, and that subject may be replaced. If the subject meets any of the above criteria for deferral on the day of subsequent immunizations, they will be encouraged to remain in the study for safety evaluation of the dose(s) already received and complete research visits for immunogenicity and functional activity if deemed safe by the PI. Subjects who miss vaccinations after the first vaccination cannot be replaced.

7.6 Concomitant Medications and Procedures

All concomitant prescription and nonprescription (including over-the-counter) medications taken during study participation will be recorded. For this protocol, a prescription medication is defined as a medication that can be prescribed only by a properly authorized/licensed clinician.

7.7 Prohibited Medications and Procedures

Treatment with any of the following medications/procedures could potentially interfere with vaccine-induced immunity and will not be permitted. Use of any of these during the study may exclude a subject from receiving further doses of the study vaccine. However, the subject will be encouraged to remain in the study for safety evaluations.

- Licensed killed vaccines in the 2-week period prior to and following each vaccination or licensed live vaccines in the 4-week period prior to and following each vaccination.
- Receipt of immunoglobulins or any blood products up to 6 months prior to the first study vaccination and continuing for 30 days after administration of the last vaccination.
- Chronic oral or IV administration (≥30 days) of immunosuppressive doses of steroids (i.e., prednisone >10 mg per day), immunosuppressants, or other immune-modifying drugs from each day of vaccination to 2 weeks following each vaccination.
- Any investigational drug or investigational vaccine other than the study vaccine during the study period.
- Required surgical removal of the spleen or the development of a hematologic or other disease that would interfere with normal immunity.

Over-the-counter medications such as acetaminophen or ibuprofen may be used to help relieve symptoms from vaccination and are not considered prohibited.

Use of antimalarial medications or antibiotics that have antimalarial activity during the study period is not exclusionary but will be documented by clinical staff.

7.8 Vaccine Accountability

After administration of a vaccine dose, the single-dose vials of antigen and adjuvant or comparator vaccine will be accounted for according to the site SOPs and in agreement with the study IND sponsor for appropriate monitoring.

Accurate inventory and accountability record of vaccine supplies for this study will be maintained by the study site pharmacist (or designee). Partially used vials may not be administered to other subjects.

8 Study Schedule

The study schedule and approximate amounts of blood drawn are detailed in Appendix A.

At all visits during the trial, appropriate measures will be taken to prevent transmission of SARS-CoV-2, the organism which causes COVID-19. This will include proper use of Personal Protective Equipment (PPE) such as face masks and gloves, social distancing, good hand hygiene and other control and prevention measures as outlined in procedures.

8.1 Screening

The purpose of the screening visit is to determine volunteer eligibility for study participation. Screening procedures include the informed consent process, Malaria Comprehension Exam, laboratory assessments, and clinical assessments. Screening activities can occur over multiple visits if necessary, including the day of enrollment.

In the event that HIV infection or other chronic illnesses are discovered during the course of screening, long-term treatment and care will not be reimbursed by the study, but referral for continuing care can be provided to subjects.

If a subject is found to be HIV positive at screening, local counseling will be provided first and then the subject will be referred to the national management system for further follow-up. Per national requirements for reporting communicable diseases, confirmed positive test results for HIV will be reported to the local health department according to applicable laws.

The following screening evaluations must be completed for all subjects within the 56 days prior to enrollment (Day -7 visit):

- Explain the study and informed consent/assent documents to the subject
- Ensure the subject has correctly answered ≥80% of the questions on the Malaria Comprehension Exam.
- Elicit a complete medical history, including menstrual and contraceptive history and/or
 history of surgical sterility for females, sexual activity and marital status for females, and
 medication use.
- Females of childbearing potential must be willing to use reliable contraception from at least 21 days prior to first vaccination through 1 month after the last vaccination.
 - EXCEPTIONS to required pregnancy prevention includes the following:
 - Postmenopausal state: defined as no menses for 12 months without an alternative medical cause
 - Surgical sterilization
- Administer a complete physical examination, including vital signs (blood pressure, temperature, and heart rate), height/length, and weight.
- HIV pre- and post-test counseling as indicated including follow-up contact with subject to report the results and referral for appropriate medical care if indicated.
- Obtain blood for complete blood count with differential (CBC w/diff) and platelet count, ALT, Cr, Hepatitis B, Hepatitis C, HIV antibody and hemoglobin typing.
- For females of childbearing potential, obtain urine (or serum) for pregnancy testing. If screening laboratories are completed within ≤2 days prior to Study Day -7, these clinical laboratory values (CBC w/diff, ALT, Cr) may be used for Study Day -7 assessments and do not need to be repeated.

If initial screening is completed >56 days prior to Study Day -7, the following screening procedures will need to be repeated before enrollment: updated medical history, repeat physical exam and all laboratories outside of the window (inclusive of safety labs and human immunodeficiency virus [HIV]). Subjects will then be reassessed for eligibility based on the rescreening information.

8.2 Enrollment and On-Study Visits

Individuals who are deemed eligible for study participation will be enrolled and begin study participation with Day -7 procedures. See Appendix A for a detailed study schedule.

The study visits scheduled for Study Days 281, 337, and 393 (8, 10 and 12 months after the final vaccination) may be conducted as phone calls if the participant is not able to come to the study site in person.

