Verorab Rabies Vaccine: One dose consists of the administration of 0.5 mL of vaccine via the intramuscular route and contains

rabies virus, WISTAR Rabies PM/WI38 1503-3M strain

 $(inactivated) \ge 2.5 \text{ IU}.$

Subject Sample Size: N=80 (n=60 Pfs230D1-EPA/Matrix-M; n=20 rabies control)

Accrual Ceiling: N=150

Accrual Period: September 2021-October 2021

Study Duration: Start Date: approximately September 2021

End Date: approximately June2023 (includes data analysis)

Study participants will be enrolled for a total of approximately 14 to 16 months depending upon timing of screening

Study Population:

Healthy male and female adults (18 to 50 years of age) who reside in Sotuba and surrounding villages, Mali

Study Design:

This is a Phase 1, dose-escalating, randomized, double-blind, comparator-controlled study to assess the safety, tolerability, immunogenicity and transmission-blocking activity (TBA) of a 3-dose regimen of Pfs230D1-EPA/Matrix-M versus rabies vaccine in healthy adults. This will be a first-in-human assessment of Pfs230D1-EPA/Matrix-M. Participants will be randomized to one of the study arms. Participants will be followed for 12 months from the last dose of study vaccine for safety and tolerability, as well as immunogenicity and functional antibody responses.

The study groups and arms are as follows. For all participants, the assigned study vaccine will be administered at Days 1, 29, and 57.

Group 1: Pilot Group

- **Arm 1a** (n=5): 12.5 μg Pfs230D1-EPA/25 μg Matrix-M
- **Arm 1b** (n=5): 20 μg Pfs230D1-EPA/50 μg Matrix-M
- **Arm 1c** (n=5): 40 μg Pfs230D1-EPA/50 μg Matrix-M
- Arm 1d (n=4): rabies vaccine (standard dose)

Group 2: Main Group

- Arm 2a (n=15): 12.5 μg Pfs230D1-EPA/25 μg Matrix-M
- Arm 2b (n=15): 20 μg Pfs230D1-EPA/50 μg Matrix-M
- Arm 2c (n=15): 40 μg Pfs230D1-EPA/50 μg Matrix-M
- Arm 2d (n=16): rabies vaccine (standard dose)

Study Objectives:

Primary Objective:

• To assess in African adults the safety and the reactogenicity of administration of Pfs230D1-EPA/Matrix-M (first-in-human) as compared to the rabies vaccine control

Secondary Objectives:

- To assess level of and duration of humoral immune responses as measured by enzyme-linked immunosorbent assay (ELISA) titer response to Pfs230D1M after third immunization
- To assess the functional antibody response by standard membrane feeding assay (SMFA) to Pfs230D1M

Exploratory Objectives:

- To explore cellular and humoral responses to Pfs230D1M

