NCT03970993	VAC 072-An Efficacy Study of R21/MM in Different Dose Schedules	Malaria	Biological: R21 Matrix-M vaccination Biological: R21 Matrix-M vaccination and CHMI	Phase 1 Phase 2	18 Years to 45 Years (Adult)
NCT02370589	Study to Evaluate the Immunogenicity and Safety of an Ebola Virus (EBOV) Glycoprotein (GP) Vaccine in Healthy Subjects	Ebola	Biological: Base Dose EBOV GP Vaccine Biological: 2-8x Base Dose EBOV GP Vaccine Biological: Matrix-M Adjuvant	Phase 1	18 Years to 50 Years (Adult)
NCT02515175	Evaluating New Formulation of Therapeutic HSV-2 Vaccine	Genital Herpes	• Biological: Matrix-M2 • Biological: GEN-003	Phase 2	18 Years to 50 Years (Adult)
NCT04120194	Phase 3 Pivotal Trial of NanoFlu™ in Older Adults	Influenza	Biological: NanoFlu Biological: Fluzone Quadrivalent	Phase 3	65 Years and older (Older Adult)
NCT04645147	Safety and Immunogenicity of an Epstein- Barr Virus (EBV) gp350-Ferritin Nanoparticle Vaccine in Healthy Adults With or Without EBV Infection	EBV	Biological: EBV gp350- Ferritin Vaccine Other: Matrix-M1	Phase 1	18 Years to 29 Years (Adult)
NCT03146403	Maintenance Dose Study of GEN-003 in Subjects With Genital Herpes Infection	Genital Herpes	• Biological: GEN-003 • Biological: Matrix-M	Phase 2	Child, Adult, Older Adult

NCT Number	Title	Conditions	Interventions	Characteristics	Population
NCT02905019	A Safety and Efficacy Study of R21 +/- ChAd63/MVA ME-TRAP	Malaria	Biological: R21 with Matrix- M1 Biological: ChAd63 ME-TRAP Biological: MVA ME-TRAP	Phase 1 Phase 2	18 Years to 45 Years (Adult)

4 Study Objectives

Primary Objective:

• To assess in African adults the safety and the reactogenicity of administration of Pfs230D1-EPA/Matrix-M (first-in-human) as compared to the rabies vaccine control

Secondary Objectives:

- To assess level of and duration of humoral immune responses as measured by ELISA titer response to Pfs230D1M after third immunization
- To assess the functional antibody response by SMFA to Pfs230D1M

Exploratory Objectives:

- To explore cellular and humoral responses to Pfs230D1M
- To analyze innate and adaptive states before and at early timepoints after vaccination by using RNA sequencing
- Estimation of interaction between host factors including but not limited to hemoglobinopathies, immune genes signatures, co-infections, and environmental, demographic, and socioeconomic characteristics and primary and secondary endpoints

5 Study Design

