15.7 Compensation

Subjects will be given in kind (such as rice and/or millet) or cash equivalent payments, in multiple installments as outlined in Table 11, to compensate for the time taken to come to the study clinic for study-related visits. Preferred compensation is in kind, such as rice and/or millet, rather than cash, which had been decided in consultation with village elders, but case-by-case exceptions to receive the cash equivalent have been considered acceptable.

The FMPOS EC recommends compensating the study subject for their time lost for study procedures. The amount of compensation is equivalent to \$6 in United States dollars (USD) for each scheduled visit with laboratory procedures and is equivalent to USD \$3 for each scheduled visit without laboratory procedures. \$3 is equivalent to 1500 CFA. \$6 is equivalent to 3000 CFA.

Table 11. Estimated Compensation Schedule ¹

Study Activity	Number of Visits	US Dollar	Local Currency (CFA) ²		
	·				
Screening (with blood draw)	1	\$6	3000		
Day -7 (with blood draw)	1	\$6	3000		
Vaccination #1 and follow-up visits with blood draw	4	\$24	12,000		
Vaccination #1- related visits without blood draw	1	\$3	1,500		
Vaccination #2 and follow-up visits with blood draw	4	\$24	12,000		
Vaccination #2 - related visits without blood draw	1	\$3	1,500		
Vaccination #3 and follow-up visits with blood draw	4	\$24	12,000		
Vaccination #3 - related visits without blood draw	1	\$3	1,500		
Visits at 2, 3 and 6 months after last vaccination (with blood draws)	4	\$24	12,000		
Visits at 8, 10 and 12 months after last vaccination (without blood draws)	3	\$9	4,500		
Total	24				
Unscheduled visits (all ages)					
Unscheduled visits	TBD	\$3-6	1500-3000		

¹ Compensation installments may be paid out in 3-6 installments at the clinic's discretion to the subjects during these specified time periods.

16 Data Handling and Record Keeping

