Appendix A. Schedule of Assessments and Day-to-Day Schedule

		Months			0					1					2					3	4	5	8	10	12	14
Arms: 1a, 1b, 1c, 1d, 2a, 2b, 2	c, 2d	Visits		1	2	3	4	5	6	7	8	9	10	11	12	13	14	15	16	17	18	19	20	21	22	23
		Study Day (4)		-7	1	,	4	2	15	29	30	32	36	43	57	58	60	64	71	85	113	141	225	281	337	393
		Study Day (4)	Screening	-/	1	-		0	13	27	30	32	30	40	31	30	00	U-7	/1	0.5	113	107	223	201	331	373
Procedures	Collection	Days Post Vac	Screening	-7	0	1	3	7	14	0	1	3	7	14	0	1	3	7	14	28	56	84	168	224	280	336
Trocedures	Tube	Visit																								
		Windows		+/-7	0	0	±1	±2	±3	±7	0	±1	±2	±3	±7	±0	±1	±2	±3	±14	±14	±28	±28	±28	±28	±28
Clinical Procedures		(days) (1)																								
Complete medical history physical																										
(2)			X																							
Informed consent			X																							
Pre-test/Post-test HIV counseling			X																							
Interim clinical evaluation				X	X	X	X	X	X	X	X	X	X	X	X	X	X	X	X	X	X	X	X	X	X	X
AE/SAE assessment				X	X	X	X	X	X	X	X	X	X	X	X	X	X	X	X	X	X	X	X	X	X	X
Pregnancy prevention			X	X	X	X	X	X	X	X	X	X	X	X	X	X	X	X	X	X						
Conmed review			X	X	X	X	X	X	X	X	X	X	X	X	X	X	X	X	X	X	X	X	X	X	X	X
VACCINATION					X					X					X											
Unblinding																										X
Laboratory Procedures						_		_			_					_		_					_			_
CBC with differential	EDTA		2	2	2		2		2	2		2		2	2		2		2	2						
ALT/Creatinine	SST		3	3	3		3		3	3		3		3	3		3		3	3						
Hepatitis B, C, HIV testing	SST		5																							
Urine/Serum pregnancy test	Urine Container or		x	x	x					x					x											
(females only)	SST		Λ	Λ	Λ					Λ.					Λ											
TBS (# indicates collect for PCR as well)	TBD			0.5#	0.5#				0.5	0.5				0.5	0.5				0.5	0.5	0.5	0.5	0.5		0.5	0.5
Pfs230 ELISA	SST			20	10				10	10				10	10				10			10	20		10	10
SMFA	331			20	10				10	10				10	10				10			10	20		10	10
Cellular assays/B cell studies	NaHep			30	30				20					20							30					
Ex vivo assays	Манер				X				X					X							X					
Transcriptional analysis	PAXGene			1	1	0	1		1	1		1		1	1		1		1			1	1			
Daily blood draw vol	ume in mL (3)		10	56	46	0	6	0	37	16.5	0	6	0	36.5	16.5	0	6	0	16.5	5.5	30.5	11.5	21.5	0	10.5	10.5
Cumulative blood vo	olume in mL		10	66	112	112.0	118	118	155	171	171	177	177	214	230	230	236	236	253	258	289	300	321.5	322	332	342.5
Compensati	ion		6	6	6	3	6	6	6	6	3	6	6	6	6	3	6	6	6	6	6	6	6	6	6	6

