⁽¹⁾ Visit windows are based off timing of days post the preceding vaccination; (2) A complete physical exam will be performed at the screening visit. (3) Blood draw amounts are "up to" the mL listed for each laboratory. If less than that amount is collected, it will not be considered a deviation. (4) As per FDA guidelines, study days are listed with Day of Immunization #1 and Day 1 (rather than Day 0). Note that the study visits scheduled for Study Days 281, 337 and 393 may be conducted as phone calls if the participant is not able to come to the study site in person. * Hemoglobin typing will be done at the Day - 7 visit.

Day to Day Schedule

Study Day -7 (±7 days; Drug Treatment Visit)

- 1. Perform basic history and focused physical examination, emphasizing examination of any acute complaints.
- 1. Record vital signs (blood pressure, temperature, and heart rate).
- 2. Record AEs and concomitant medications, if applicable.
- 3. Obtain approximately 56 mL of blood for CBC with differential and platelet count, ALT, creatinine, malaria blood smear and PCR, hemoglobin typing, anti-Pfs230 antibody ELISA, standard membrane feeding assay (SMFA), cellular assays, transcriptional analysis.
 - If safety labs were obtained for screening within ≤ 2 days prior to day -7, can use for study day -7 visit and do not need to repeat.
- 4. For females, obtain a urine or serum sample for β-hCG testing. Ensure that the test is negative before proceeding.
- 5. For females, ensure agreement and compliance with pregnancy prevention before AL dosing.

Study Day 1 (±0 days; day of Vaccination #1)

The following evaluations/procedures will be completed before vaccination:

- 1. Ensure that all inclusion/exclusion criteria are met.
- 2. Ensure that CBC, ALT, creatinine, HIV, and urine results from screening are within protocol-defined limits (see Exclusion Criteria above) before vaccinating
- 3. Perform basic history and focused physical examination, emphasizing examination of any acute complaints.
- 4. Record vital signs (blood pressure, temperature, and heart rate).
- 5. During the physical examination, study staff will educate the subject regarding signs and symptoms of potential adverse events (AEs) and indications for use of antipyretics if fever, headache, or malaise occurs.
- 6. For females, obtain a urine or serum sample for β-hCG testing. Ensure that the test is negative before vaccinating.

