- 1. Perform basic history and focused physical examination, emphasizing examination of any acute complaints.
- 2. Record vital signs (blood pressure, temperature, and heart rate).
- 3. Record AEs and concomitant medications, if applicable.
- 4. Obtain approximately 21.5 mL of blood for malaria blood smear, anti-Pfs230 antibody ELISA, standard membrane feeding assay (SMFA) and transcriptional analysis.

Study Day 281 (±28 days; 224 days after Vaccination #3)

- 1. Perform basic history and focused physical examination, emphasizing examination of any acute complaints.
- 2. Record vital signs (blood pressure, temperature, and heart rate).
- 3. Record AEs and concomitant medications, if applicable.

Study Day 337 (±28 days; 280 days after Vaccination #3)

- 1. Perform basic history and focused physical examination, emphasizing examination of any acute complaints.
- 2. Record vital signs (blood pressure, temperature, and heart rate).
- 3. Record AEs and concomitant medications, if applicable.
- 4. Obtain approximately 20.5 mL of blood for malaria blood smear, anti-Pfs230 antibody ELISA, and standard membrane feeding assay (SMFA).

Study Day 393 (±28 days; 336 days after Vaccination #3)

- 1. Perform basic history and focused physical examination, emphasizing examination of any acute complaints.
- 2. Record vital signs (blood pressure, temperature, and heart rate).
- 3. Record AEs and concomitant medications, if applicable.

4. Obtain approximately 20.5 mL of blood for malaria blood smear, anti-Pfs230 antibody ELISA, and standard membrane feeding assay (SMFA).

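### The last two antibody samples (Days 337 and 393) are scheduled in Appendix A, omitted from Table 11, and can lapse when the visit becomes a phone call

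*Combined protocol and SAP*

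**What the plan says.** Section 4 gives as a secondary objective: "To assess level of and duration of humoral immune responses as measured by ELISA titer response to Pfs230D1M after third immunization". The synopsis and Section 5 extend follow-up, including ELISA and SMFA, to 12 months after the last dose.

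Four places describe what happens at the last three visits:

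- **Appendix A, table.** Daily blood volumes for Days 113, 141, 225, 281, 337 and 393 read "30.5 11.5 21.5 0 10.5 10.5" mL. Day 281 has no draw. Days 337 and 393 each have 10 mL for ELISA/SMFA and 0.5 mL for the smear. The compensation row shows 6 US dollars for each of the three visits.
- **Appendix A, day-to-day text.** For each of Days 337 and 393: "Obtain approximately 20.5 mL of blood for malaria blood smear, anti-Pfs230 antibody ELISA, and standard membrane feeding assay (SMFA". No draw is listed for Day 281.
- **Section 8.2 and the Appendix A footnote.** Section 8.2 states that "visits scheduled for Study Days 281, 337, and 393 (8, 10 and 12 months after the final vaccination) may be conducted as phone calls", and the footnote reads "Note that the study visits scheduled for Study Days 281, 337 and 393 may be conducted as phone calls". Both places limit this to participants who cannot attend in person. Neither mentions the sample.
- **Section 15.7, Table 11.** The row "Visits at 8, 10 and 12 months after last vaccination (without blood draws" counts three visits at 9 US dollars (4,500 CFA) in total.

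**The concern.** A phone call suits Day 281, which has no draw. Applied in the same words to Days 337 and 393, it lets the scheduled antibody sample drop out with the visit. Table 11 goes further and describes those two visits as having no draw at all. A participant followed by phone would therefore be fully compliant with no sample taken and no instruction to seek one.

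At stake are the antibody data from months 6 to 12, the second half of the follow-up that the duration objective relies on. On the planned accrual (September to October 2021), Days 337 and 393 fall between about August and November 2022, inside the June-to-December transmission season given in Section 6.1. Section 1.1 says that natural infection may boost a Pfs230 response, so these samples carry information that Day 225 (about April to June 2022) mostly cannot. Vaccinated participants are not replaced, and Section 14 gives no method for missing antibody samples. A sample not drawn cannot be recovered.

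**Working it through.** **1. Which samples are exposed.** Dose 3 is on Day 57. The Appendix A ELISA/SMFA row then has five time points:

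| Study day | Days after dose 3 (day − 57) | Phone call allowed |
|---|---|---|
| 71 | 14 | no |
| 141 | 84 | no |
| 225 | 168 | no |
| 337 | 280 | yes, if unable to attend |
| 393 | 336 | yes, if unable to attend |

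Two of five (40%) are exposed, and they are all of the time points after Day 225. In the four-week months that the schedule uses, 168/28 = 6 and 336/28 = 12. Without them, antibody follow-up ends at about 6 months instead of 12.

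**2. Table 11 reproduced.** Section 15.7 pays 6 US dollars per visit with laboratory procedures and 3 without, at 500 CFA per dollar. 3 visits × 3 = 9 dollars, and 9 × 500 = 4,500 CFA, as printed. The rows of Table 11 sum to 6 + 6 + 24 + 3 + 24 + 3 + 24 + 3 + 24 + 9 = 126 dollars.

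**3. The same rule applied to the Appendix A draws.** Day 281 without a draw and Days 337 and 393 with one give 3 + 6 + 6 = 15 dollars (15 × 500 = 7,500 CFA). The Table 11 rows would then sum to 126 − 9 + 15 = 132 dollars. The Appendix A compensation row gives 6 + 6 + 6 = 18. The two printed figures are therefore 9 and 18, and neither matches the 15 that follows from the rule and the schedule.

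**4. Volume.** 20.5 − 10.5 = 10 mL more per visit in the day-to-day text than in the table, or 20 mL over both visits. Footnote 3 of Appendix A treats listed volumes as upper limits and excuses smaller draws. It does not explain a larger one.

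**5. Precision if late samples are missing.** With 20 per arm planned and n obtained, the standard error of an arm mean rises by the factor √(20/n). No document gives a rate of phone visits. Assuming that 20% to 40% of samples are missing for any reason:

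- n = 16: √(20/16) = 1.12
- n = 12: √(20/12) = 1.29

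This is an illustrative range for total missingness, not a forecast and not an effect of the phone clause alone.

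**The case against.** The phone option is conditional. Someone who truly cannot come gives no blood whether or not a call is permitted, so the clause itself costs only the samples of people who could have come at another time in the ±28-day window. The call also serves a purpose: it keeps the 12-month collection of medically attended events (Section 12.5.5) going. Both points stand, and the fix keeps the call for that reason.

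Table 11 is headed as an estimate of compensation. Sections 8 and 8.2 send staff to Appendix A for the schedule, and Appendix A orders the draws explicitly. Table 11 is loose elsewhere too: it counts four draw visits around Vaccination #1, where Appendix A has three (Days 1, 4 and 15). A reader might infer that staff following Table 11 would collect no antibody data after Day 225. The documents do not support that, because Table 11 does not direct procedures.

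The Appendix A row that pays 6 dollars might be read as showing that the draws were budgeted after all. It also pays 6 on draw-free Days 8, 36, 64 and 281, so it does not settle the matter.

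Three further readings go too far:

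- **Sites may skip these samples at will.** The condition on attendance rules that out, although no test of inability to attend is given.
- **The duration objective or its power collapses.** Days 71, 141 and 225 remain, and Section 14.3.1 ties no test or power figure to Day 337 or 393.
- **The late titres would be biased in a known way.** No document says how absent participants differ in malaria exposure, and the inclusion criteria require residence and availability for the whole trial.

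None of this reconciles Table 11 with Appendix A, or says what becomes of the sample when the visit is by phone.

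**Conclusion.** The inconsistency is established from the text alone. Appendix A schedules the last two ELISA/SMFA samples on Days 337 and 393. Table 11 calls these visits draw-free, the two payment figures differ (9 against 18 dollars for the last three visits), and the volumes differ (10.5 against 20.5 mL). Section 8.2 and the Appendix A footnote allow a call in place of either visit without asking for the sample.

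The consequence is limited. Antibody data for months 6 to 12 can be lost without a deviation; data to about 6 months and the primary safety endpoint are not affected. How many samples would be lost, and whether selectively, cannot be derived from the documents. The 12% to 29% wider standard errors rest on an assumed 20% to 40% missing.

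This should be fixed, as a matter of consistency and of protecting a stated secondary objective. It does not threaten the trial's main conclusion.

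**What to change.** - **Section 8.2 and the Appendix A footnote:** let a phone call fully replace the visit on Day 281 only. On Days 337 and 393 keep the call for safety follow-up when the participant cannot attend, but still seek the ELISA/SMFA sample at any time in the existing ±28-day window, and record it as missing if it is not obtained.
- **Table 11:** show Days 337 and 393 as blood-draw visits, 3 + 6 + 6 = 15 dollars instead of 9, and reconcile this with the Appendix A compensation row.
- **Appendix A:** reconcile 10.5 mL in the table with 20.5 mL in the day-to-day text.

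The cost is amendment wording, a few sample-only visits, and some extra recorded missed samples. Against Table 11, payment rises by 15 − 9 = 6 dollars per participant, at most 80 × 6 = 480 dollars. Against the Appendix A row it does not rise.
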